IECSCYL-IBSAL	Foundation of the Institute of Health Sciences Studies of Castilla y León- Institute of Biomedical Research of Salamanca
MIR	Hospital resident
MPL	Monophosphoryl lipid
ORP	Occupational Risk Prevention
NHS	National system of health
HBV	Hepatitis B virus

1. Summary

- **Study promoter:** Fundación Institute of Health Sciences Studies of Castilla y León (IECSCYL) -Institute of Biomedical Research of Salamanca (IBSAL). IECSCYL-IBSAL Foundation
- **Study title:** VACCINATION ADJUVED AGAINST HEPATITIS B IN SNS WORKERS TYPED AS NO RESPONDERS TO CONVENTIONAL VACCINES.
- **Protocol code:** IBS-VACANTIB-1701
- **EudraCT number:** 2016-004991-23
- **Study coordinator and direction:**

[name] [name]
Head of the Occupational Risk Prevention Service

Salamanca University Hospital [name]
ZIP: 37007 Salamanca
- **Telephone [contact]. [name]
- **Direction of e-mail:** [contact]
- **Participating centers**
 - University Clinical Hospital from Valladolid.
 - Healthcare Complex of Zamora.
 - University Healthcare Complex of Lion.
 - University Healthcare Complex of Palencia.
 - University Healthcare Complex of Salamanca. (Coordinating Center)
- **CEIm evaluating the study:**
 - CEIm Salamanca Health Area (Healthcare University Complex of Salamanca).
- **Main goal:**
 - Benefit and equip NHS staff with an additional protection tool against hepatitis B infection.

- To evaluate the efficacy of the adjuvanted vaccine in healthy subjects not responding to the conventional hepatitis B vaccine.
- **Design:** Open, multicenter, low-level clinical trial.
- **Pathology or study disorder:** NHS workers, including university students who carry out their internships in health centers of the National Health System (inclusion of students is subject to and limited by the specific instructions on occupational prevention in each autonomous community) with biological risk in their tasks, which have been classified as non-responders to vaccination against Hepatitis B.
- **Facts about study medication:** Fendrix® is a hepatitis B vaccine containing HBsAg adjuvanted by 3-O-desacyl-4'-monophosphoryl lipid A and with aluminum phosphate. This adjuvant system is called AS04C and increases the immunogenicity of the vaccine. An anti-HB antibody titer ≥ 10 mIU / mL correlates with protection against HBV infection.
- **Population study and total number of patients:** Workers from the health field of the NHS, with biological risk in their tasks, who have been classified as non-responders to vaccination against Hepatitis B. Initial estimate of up to 80 subjects in total included in the study among all centers.
- **Key dates of the study**
 - Start of study (PVPP)- April 2018
 - The end Inclusion (PVUP) - May 2019
 - The end study (UVUP) - December 2019
 - Ending of the Clinical Study Report (IEC) - February 2020
 - Date Publication - April 2020
- **Sources financing**
 - Projects research. Castilla and leon meeting. Ministry of Health. GRS 1360 / A / 16.
 - Sponsor's own funds dedicated to promoting Clinical Research.

2. Index

ABSTRACT OF THE STUDY.....	two
Acronyms.....	5
1. SUMMARY	6
2. INDEX.....	8
3. INFORMATION GENERAL.....	9
4. JUSTIFICATION FROM THE STUDY: CRITICAL REVIEW OF THE LITERATURE	10
5. OBJECTIVES	13
6. SOURCEAND INFORMATION FIELD.....	13
7. STUDY DESIGN.....	13
8. CRITERIAVALUATION AND MEASURING INSTRUMENTS	18
9. STATISTIC ANALYSIS	18
10. ETHICAL ASPECTSAND LEGAL	19
11. CONSIDERATIONSPRACTICES	22
12. UTILITYPRACTICE OF RESULTS IN RELATION TO HEALTH	26
13. REFERENCESBIBLIOGRAPHICS	28
14. ANNEXES	29

3. General information

- **Protocol code:** IBS-VACANTIB-1701
- **Title:** VACCINATION ADJUVED AGAINST HEPATITIS B IN SNS WORKERS TYPED AS NO RESPONDERS TO CONVENTIONAL VACCINES
- **Study promoter:** IECSCYL-IBSAL Foundation
- **Telephone [contact]
- **Direction of e-mail:** [contact]
- **Principal investigator:**

[name] [name]
Head of the Occupational Risk Prevention Service at the
Salamanca University Assistance Complex
- **Participating centers**
 - University Clinical Healthcare from Valladolid.
Address: [name]
Town: Valladolid CP: 47005
 - Healthcare Complex of Zamora.
Address: [name] Town:
Zamora Zip Code: 49021
 - University Healthcare Complex of Lion.
Address: [name]
Town: León ZIP: 24071
 - University Healthcare Complex of Palencia.
Address: [name]
Town: Palencia CP: 34004
 - University Healthcare Complex of Salamanca. (Coordinating center)
Unit: Salamanca Healthcare Complex
Address: [name]
- **Trial duration:** 2 years

4. Study justification: Review criticism of literature

Currently there is no effective solution for health workers who have not responded to two complete guidelines for hepatitis B vaccine and are exposed to developing Hepatitis B virus infection, because of a biological accident (due to needle stick, splashing, etc ...) when encountering fluids from a source patient with a situation of virus transmissibility.

The probability of contagion after a puncture, it is estimated between 7 - 30% in the presence of a positive source of hepatitis B virus (HBV). It is the most contagious hepatitis and is fulminant in 1-2% of cases, with a mortality between 63-93%. It progresses to chronicity in 10% of acute infections and can lead to occupational disease / disability.

The health and non-health worker population of the NHS has a real risk of contracting this infection, especially the unvaccinated groups and those classified as "non-responders"; understood as such, those people who have received two complete schedules of three doses of conventional vaccine (trade name Engerix®) for hepatitis B at doses of 20 µg / mL (total six doses). The percentage of non-response for this traditional vaccine is between 5-10% of those vaccinated, with titers of Ab Anti HBs less than 10 mIU / ml. The lack of response to standard vaccination is influenced by the following characteristics:

- Age: over 40 years old
- Gender: Male
- BMI > 30
- Smokers
- Chronic illness
- Immunodeficiency
- Some HLA haplotypes.

Although there is the possibility of applying specific anti-hepatitis B Gamma Globulin in the case of a biological accident, as a remedy indicated in 'unvaccinated' and likewise in 'non-responding' workers, it seems logical that a vaccine alternative could be offered these workers from which they may be beneficiaries.

 - Average at two months:
 - 575.23 mIU / mL of respondents (95%) (n = 19)
 - Between > 1000 and 25.67
 - Average per year:
 - 175.18 mIU / mL of respondents (75%) (n = 15)
 - Between > 1000 and 14.22
 - Adverse Effects: General malaise and fatigue with the first dose, and the rest well (2 people), no data: 7 people, like any vaccine (1 person), local pain, which subsided in a few days (10 people)
 - Non Responders: one person

The Conclusions of this preliminary study of vaccination with adjuvanted hepatitis B vaccine (rDNA) is that it is well tolerated clinically, its conversion values are excellent, although the sample is still insufficient to extract definitive data and the behavior in healthy individuals seems to be different from other with pathologies that are

compromised with the immune response.

In relation to the inclusion of the population of university students who carry out their practices in health centers of the National Health System, Even though the trainees have no employment relationship of any kind with the NHS Managements in which they carry out their training activities, they may be subject to the same or similar risks as the workers with whom they carry out their training practices.

Royal Decree 1707/2011, of November 18, which regulates the external academic practices of university students, establishes a series of rights and duties of the student and the collaborating entity in matters of risk prevention and occupational health.

Among them is the student's right to receive, from the collaborating entity, information on the safety regulations and prevention of occupational risks (art. 9 1.f), as well as the duty to (...) respect the rules of operation, safety and prevention of occupational hazards (art.9 2.d).

In relation to the tutor of the collaborating entity, it determines that he / she will have the duty to inform the student of the organization and operation of the entity and of the regulations of interest, especially those related to safety and occupational risks (art. 11 1c).

For its part, Directive 2010/32 / EU of May 10, 2010, which applies the Framework Agreement for the prevention of injuries caused by sharp instruments in the hospital and health sector and article 6 of Order ESS / 1451/2013, of July 29, which transposes the previous Directive, establishes that "vaccination must be offered free of charge to all workers and students who carry out health and related activities in the workplace": In the case of not acceptance of the offered vaccination must be recorded in writing of this decision.

The inclusion of this population of university students will be subject to the specific instructions on occupational prevention in each autonomous community. In the case of centers located in the Community of Castilla y León, their inclusion will be made based on the document "Instructions of the Ministry of Health of the Junta de Castilla y León of October 11, 2013" (link: http://www.sanidad.ccoo.es/comunes/recursos/15617/doc287408_Instruccion_de_la_gerenciaRegional_de_Salud_sobre_adopcion_de_medidas_de_prevencion_de_riesgos_y_salud_laboral_para_los_estudiantes_que_realizan_sus_practicas_df_que_realizan_sus_practicas_df

Therefore, it is proposed to carry out a broader study involving as collaborators several hospitals belonging to the NHS and the expansion of the target population.

5. goals

- **Main goal**

1. Benefit and equip NHS staff with an additional protection tool against hepatitis B infection.
2. To evaluate the efficacy of the adjuvanted vaccine in healthy subjects NON-responders to the conventional hepatitis B vaccine.

- **Secondary objectives**

1. Analyze results of anti-HBs antibody titers to see the immune response to the adjuvanted vaccine.
2. Evaluate safety results and clinical tolerance of the adjuvanted vaccine.

6. Source and information field

The source and field of information will be the electronic data collection notebook (ECRFe) that the researcher will fill in based on the patient's medical history.

7. Trial Design

- **Design:** open, multicenter clinical trial with use of off-label medication.
- **Duration:** 2 years
- **Ambit study:** Services of Prevention of Occupational Risks of the public hospitals of the NHS

The multicenter trial will be carried out in the following hospital centers:

- University Clinical Hospital from Valladolid. ([name] [name])
- Healthcare Complex of Zamora. ([name] [name])
- University Healthcare Complex of Lion. ([name] [name])
- University Healthcare Complex of Palencia (Dra. [name])
- University Healthcare Complex from Salamanca ([name] [name], (Coordinating Researcher)

The trial features one investigator coordinating the project and one principal investigator per hospital, who in turn will have the collaboration of teams belonging to the Occupational Risk Prevention Service.

- **Population study: selection criteria**

University workers and students from the health field of the NHS, with biological risk in their tasks, who have been classified as non-responders to vaccination against Hepatitis B. Initial estimate of a maximum of 80 subjects in total included in the trial among all centers.

Criteria inclusion:

- Workers of the NHS -including university students who carry out their practices in health centers dependent on the National Health System (inclusion of students is subject and limited by the specific instructions on occupational prevention in each autonomous community).
- In working age.
- No diseases that would contraindicate vaccination with Fendrix®.
- Criteria that define them as NOT responders to the conventional hepatitis

B vaccine: anti-HBs Ab titers <10 mIU / ml after the application of six doses of conventional vaccine at doses of 20 µg (two complete regimens)

- Subjects signing informed consent

Criteria of exclusion:

- Known allergy the active ingredient or any of the other ingredients of the medicine (included in section 6 of the product's technical sheet).
- If you have ever had an allergic reaction to any hepatitis B vaccine
- If you have a severe infection with a fever.
- Subjects of which informed consent is not obtained
- Subjects that have not revoked the initially signed consent.

• Informed consent:

Prior to the administration of the vaccination schedule, the worker will be informed of the purpose of said vaccination indication, its possible benefits and risks derived from its use, requesting the completion of a specific informed consent.

• Withdrawal criteria and scheduled analysis of withdrawals and dropouts

The patients they can leave the trial at any time and for any reason, without this having any negative effect on their aftercare.

Although the patient is not obliged to provide any explanation for leaving the trial prematurely, the investigator will reasonably attempt to determine the patient's motives, always respecting their rights. If a patient leaves the trial prematurely, the final visit data will be recorded in the ECRF.

The doctor may suspend the treatment at any time during the follow-up and replace it with another drug that he considers more beneficial for the patient, immediately informing the promoter of the trial.

• Treatment description and definition of exposure

Product description:

Fendrix® is a hepatitis B vaccine that contains HBsAg adjuvanted by 3-O-desacyl-4'-monophosphoryl lipid A and with aluminum phosphate. This adjuvant system is called AS04C and increases the immunogenicity of the vaccine.

- Generic name: Vaccine of Hepatitis B adsorbed and adjuvanted by AS04C
- Trade name: Fendrix®
- Laboratory: Glaxo Smithkline
- ATC therapeutic group: J07BC (Hepatitis Vaccines)
- Form of presentation: 20 µg pre-filled syringes

Fendrix® is a hepatitis B vaccine that contains HBsAg adjuvanted by 3- O-desacyl-4'-monophosphoryl lipid A and with aluminum phosphate. This adjuvant system is called AS04C and increases the immunogenicity of the vaccine. An anti-HB antibody titer \geq 10 mIU / mL correlates with protection against HBV infection. It is indicated for active immunization against infection by all known subtypes of Hepatitis B virus in patients with renal failure (including pre-hemodialysis and hemodialysis patients) older than 15 years. However, it is intended to take advantage of the greater immunogenic capacity

of this vaccine in non-responders, understood as those who have received two complete vaccination schedules without reaching an antibody titer greater than 10 mIU / mL.

Terms of administration:

Immunization will consist of a maximum of 4 doses of 0.5 ml administered according to the following schedule: 1 month, 2 months and 6 months from the date of the first dose, with an intramuscular vial in the deltoid muscle at the dose of 20 μ g, as stated in the Fendrix technical data sheet. After the administration of each of the doses, a serological analysis will be carried out (approximately 30 days after the administration of each dose), making it clear that if seroprotection is achieved (anti-HB \geq 10 mIU / ml, the administration will be suspended. of successive doses.

The precautionary measures regarding contraindications and warnings of the product, recommended by the manufacturer and in accordance with the recommendations of the AEMPS for its use outside the technical data sheet, will be observed.

• Stages developmental

Stage 1:

- Start up:
 - Elaboration of the documentation of the final trial: latest version of the Protocol, Electronic Data Collection Notebook (ECRFe), Informed consent for the subject, etc.
 - Request to the AEMPS classification of clinical trial and recommendations for the use of the drug outside of the technical data sheet.
 - Obtaining of CEIms authorizations and necessary contracts with the centers: carried out by the Salamanca Hospital and the IBSAL (Technical Management Unit of the Salamanca Biomedical Research Institute-clinical trials area).
- Preselection of candidates (8 weeks) in the collaborating centers of:
 - Valladolid University Clinical Hospital.
 - Zamora Healthcare Complex.
 - León University Healthcare Complex.
 - Palencia University Healthcare Complex.
 - Salamanca University Healthcare Complex.

Pre-select the workers described in the target population based on the records obtained from their clinical-working histories, which have received 6 doses of conventional hepatitis B vaccine and have not exceeded 10 mIU / mL. Detection of new cases at the University Hospital of Salamanca.

Stage 2:

- Purchase of medication: coordinated from the IBSAL-Hospital de Salamanca.

- Transport of medication to the collaborating centers: from a commercial provider to the Occupational Risk Prevention Services of the participating centers.

Stage 3:

- Inclusion of participating subjects: recruitment in each center. Select the workers described in the target population based on the records obtained from their clinical-working histories, who have received 6 doses of conventional hepatitis B vaccine and have not exceeded 10 mIU / mL.
- Dosage administration, evolution monitoring and safety: Once the consent of the participant has been obtained, Fendrix® will be prescribed at a dose of 20 micrograms up to a maximum of 4 doses. The antibody titer per month of each dose of vaccine administered will be subsequently analyzed locally at each center. Possible events and adverse reactions will be detected, subsequently monitoring the applicable Pharmacovigilance.

Visits calendar from the patients:

Visits	Selection Visit	Visit1	Visittwo	Visit3	Visit4	Final visit
Time		Month0	Month1	Month 2	Month6	Month7
Procedures and tests						
Pick up of data and tests required for the test	X					
Analytics	X		X	X	X	X
Drug administration		X	X	X	X	
Pick up of data related to other medications and adverse events		X	X	X	X	X
Completion sheet						X

Stage 4:

- Compilation of the analyzes and ECRFs from the collaborating centers to the coordinating center.
- Treatment of data and statistical analysis: coordinating center-IBSAL.

Stage 5:

- **Publication:** from the coordinating center.

- **Schedule. Plan of work**

Activity:	People involved	From (mm / yyyy)	Until (mm / yyyy)
Stage 1	8	Jan-2017	Dec-2018
Stage 2	6	May-2017	Feb-2019
Stage 3	8	Jun-2017	Jun-2019
Stage 4	7	Dec-2018	Dec-2019
Stage 5	6	Jan-2019	Apr-2020

- **Available media to carry out the test.**

The infrastructure where it will be carried out resides in the prevention services of the hospitals involved. In addition to the management support for its development by IBSAL in its Technical Management Unit (HU Salamanca). In these services there are adequate facilities, material means to carry out all the processes required for the development of the test (refrigerators, determinations of Ab, etc.)

The personnel involved in the trial are NHS personnel with extensive experience in Occupational Risk Prevention in the health field, in addition the trial will receive the necessary administrative management support from the Clinical Trials Area of the IBSAL Technical Management Unit

- **Limitations of the trial**

The main limitation of the trial will be to find new cases of non-responding workers and overcoming the difficulties of the lack of standardized records of non-responding workers from the different prevention services of the collaborating hospitals.

8. Valuation criteria and measurement instruments

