8.2. Variables to study

- Measurement of the anti-HBs antibody titer: before the first dose and one month after the administration of each dose.
- Pickup of adverse effects during administration and all those that could be

related to the vaccine and that appear within 30 days after each dose.

9. Statistical analysis

A statistical analysis of the data will be carried out, assisted by the IBSAL Biostatistics Research Group

- Sample size justification**

The sample size is based on the recruitment carried out from the previous study carried out at the Salamanca University Healthcare Complex. Considering the number of subjects susceptible to study in the different centers, a sample size of up to 80 subjects is estimated.

- Statistical methodology**

The results of the present trial and the clinical-biological data of the patients will be registered in a database.

Statistical significance: The results will be analyzed using SPSS software (version 15.0) for Windows.

An initial descriptive analysis of the quantitative variables will be carried out, which will include measures of central tendency (mean, median), measures of dispersion (range, standard deviation) and box plots, with possible extreme values. For qualitative variables, frequencies will be presented.

The level of significance will be set at $p < 0.05$.

10. Ethical aspects and legal

The researcher will carry out the study in compliance with the ethical principles of the Declaration of Helsinki.

The trial must adhere to the protocol, which guarantees compliance with Good Clinical Practices, described in the Harmonized Tripartite Guidelines of the ICH on Good Clinical Practices.

This trial will be submitted for evaluation by a Drug Research Ethics Committee and the Spanish Agency for Medicines and Health Products (AEMPS) will be notified.

The pertinent authorizations will be obtained in accordance with current regulations for clinical trials.

- Information sheet and consent form**

The researcher will explain to each patient (witness or legal representative) the nature of the trial and the purposes, procedures, estimated duration, possible risks and benefits of participating in the trial and possible inconveniences that it may cause. All patients will be informed of the voluntary nature of their participation and that they may withdraw at any time, without affecting their future medical care or their relationship with the doctor responsible for their treatment.

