The Ethics Committee for Drug Research (CEIm) will review the protocol, the proposed informed consent form and other information for patients. Any modification of the protocol, apart from administrative changes, will require an amendment to the protocol that must be approved by said Committee. Changes in the direction of the trial that are not accompanied by an amendment will be considered deviations. Deviations may lead to disqualification of the center from continuing to participate in the trial.

11. Practical considerations

- **Study plan and inclusion of patients**

The patients will be selected and, once informed consent has been obtained and verified that the patient meets the selection criteria, the information will be recorded in the ECRF and the samples provided will be analyzed.

- **Procedures for the communication of adverse reactions**

An adverse event is the appearance of signs, symptoms, or an undesirable medical pathology (or the worsening of the pre-existing ones) that occurs after the signing of the informed consent, even if the event is not considered related to the treatment.

An adverse drug reaction is the appearance of signs, symptoms, or an undesirable medical condition in a patient receiving a drug that is considered drug related.

Serious adverse event

To ensure patient safety, any serious adverse event (SAE), regardless of suspected causation, that occurs after the patient has given informed consent and up to 4 weeks after treatment / patient participation has been discontinued. the trial, the researcher will send the completed SAE / pregnancy form (Annexes 4 and 5), in the first 24 hours from its knowledge to the Pharmacovigilance Node (UICEC Hospital Universitario de Canarias). [contact] or by email to: [contact]. . The original and duplicate copies of the SAE Form, and the fax confirmation sheet, will be kept at the trial site, along with the data collection notebooks.

ASAE is defined as an event that:

- Cause death or life threatening.
- Causes a disability/ persistent or significant disability.
- It constitutes a congenital anomaly / birth defect.
- Requires hospitalization or the prolongation of a pre-existing hospitalization, unless the hospitalization is due to:
 - to routine treatment or to the control of the studied indication, without deterioration of the pathology (specify what it includes)

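### The visit calendar schedules no adverse-event collection between dose 3 (Month 2) and Month 6, although the safety window is 30 days and a titer is due near Month 3

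*Combined protocol and SAP*

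**What the plan says.** Section 7 (terms of administration) allows up to four doses, the later ones at "1 month, 2 months and 6 months from the date of the first dose". It asks for serology "approximately 30 days after the administration of each dose" and stops further doses once seroprotection is reached. Stage 3 of the same section again places a titer a month after each dose. On safety it says only: "Possible events and adverse reactions will be detected, subsequently monitoring the applicable Pharmacovigilance".

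The visit calendar in section 7 has a selection visit and columns for Months 0, 1, 2, 6 and 7. Vaccine is marked at Months 0, 1, 2 and 6. Blood tests are marked at selection and at Months 1, 2, 6 and 7. The row "Pick up of data related to other medications and adverse events" is marked at Months 0, 1, 2, 6 and 7. There is no Month 3 column.

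Section 8.2 sets the titer at "before the first dose and one month after the administration of each dose". It defines the safety variable as effects during administration and those that could be "related to the vaccine and that appear within 30 days after each dose". Section 5 makes safety and clinical tolerance a secondary objective. Under section 11, serious events have their own route: a form is sent "in the first 24 hours from its knowledge to the Pharmacovigilance Node".

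**The concern.** The safety variable has the same 30-day window for every dose, but the calendar does not observe every dose on the same terms. After doses 1, 2 and 4 the next scheduled collection falls as the window closes. After dose 3 it falls about three months later. Sore arms, malaise and fatigue are short-lived and easily forgotten, and they are what a tolerance summary mostly counts. A lower reported rate after dose 3 could then reflect the longer recall period rather than better tolerance, and the data could not separate the two.

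The vaccine is used outside its authorized indication, so tolerance in this population is part of what the trial adds. Dose 3 goes only to subjects not yet seroprotected, out of at most 80, so each lost report may weigh more in the dose-3 summary.

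**Working it through.** The plan states no figure for the interval from a dose to the next safety collection, so there is none to reproduce. It can be derived from the calendar.

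Inputs:
- Dose months: 0, 1, 2, 6 (section 7, terms of administration and calendar).
- Adverse-event collection months: 0, 1, 2, 6, 7 (section 7, calendar).
- Safety window: 30 days after each dose (section 8.2).
- Conversion: 30.44 days per month (my convention).

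Formulas: gap = next collection month after the dose − dose month; lateness = gap in days − 30.

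| Dose | Month given | Next collection | Gap | Days | Days after window closes |
|---|---|---|---|---|---|
| 1 | 0 | 1 | 1 month | 30 | 0 |
| 2 | 1 | 2 | 1 month | 30 | 0 |
| 3 | 2 | 6 | 4 months | 4 × 30.44 ≈ 122 | 122 − 30 = 92 |
| 4 | 6 | 7 | 1 month | 30 | 0 |

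Next, the text against the calendar. The titer rule in sections 7 and 8.2 puts a sample near Month 2 + 1 = Month 3. The calendar's first blood test after dose 3 is at Month 6. The two cannot both be followed as written. If collection were also marked at Month 3, the dose-3 gap would be 3 − 2 = 1 month, about 30 days, the same as for the other doses.

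Share of doses affected: the documents do not say how many subjects will reach dose 3. If all 80 received four doses, dose 3 would be 80/320 = 25% of doses. If all 80 stopped after three, it would be 80/240 = 33%. If few needed dose 3, the share would be close to zero.

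Size of under-recording: not computable, because the documents give neither a reaction rate for this regimen nor a recall rate. As an illustration only, assume half of dose-3 recipients react and between 50% and 100% of those reactions are still recorded at Month 6. With 20 recipients, 5 to 10 of 10 reactions would be recorded; with 80, 20 to 40 of 40. The width of these ranges comes entirely from the assumed recall rate.

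**The case against.** The strongest reply is that a Month-3 contact already exists in substance, because the text requires a titer about 30 days after dose 3 and staff would naturally ask about reactions then. The first half stands: the documents imply the contact, so this is mainly a conflict between text and calendar. The second half does not. No section assigns safety collection to that contact, and a site that follows the calendar will not hold it.

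It can also be said that the gap concerns one dose and a secondary objective, and that section 9 plans only descriptive statistics with no comparison between doses. Because dosing stops at seroprotection, dose-3 recipients are a selected group in any case. All of that stands and limits the weight of the point. A descriptive dose-3 rate would still rest on a longer recall period than the others.

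Several stronger readings are tempting but lack support:
- A reader might infer that events are gathered only by questioning at visits, or that the data form cannot record that a subject was asked and had none. The protocol names no method of elicitation. Section 6 has the form completed from the medical history, and the form's manual and the patient information sheet are separate documents that are not available here.
- A reader might infer from the earlier Salamanca study, with "no data: 7 people" out of 20 on adverse effects, that the weakness is already demonstrated. That study used a different regimen (40 µg at months 0, 1 and 6), and how its tolerance data were collected is not stated. Its missing data give no magnitude for this calendar.
- A reader might infer that serious events after dose 3 would go unnoticed for months. The 24-hour limit does run from the investigator's knowledge. But subjects are staff or students followed by hospital prevention services, and nothing in the documents shows that such events would stay unknown.

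**Conclusion.** The point holds as a scheduling gap with an internal contradiction behind it. By the calendar, the first scheduled adverse-event collection after dose 3 comes at four months, about 92 days after the safety window closes, against one month for each other dose. The text requires a titer near Month 3 that the calendar omits, and no safety collection is attached to it.

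Mild reactions after dose 3 are at risk of being under-recorded relative to the other doses. That they will be is not shown, and no size can be given. The gap reaches only subjects who receive dose 3. The documents also leave open whether someone who stops dosing after the post-dose-3 titer still attends Months 6 and 7. If not, the calendar offers that subject no scheduled safety collection after dose 3 other than whatever final-visit data are recorded.

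This rests on reading the calendar as the full list of scheduled collections and on the separate annexes adding no further one.

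**What to change.** Reconcile the titer timing in section 7 (terms of administration and Stage 3) and section 8.2 with the visit calendar. Add the contact near Month 3 to the calendar for every subject who receives dose 3, whether or not dosing continues. Mark adverse-event and concomitant-medication collection at that contact, by telephone if the sample is not taken in person.

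In the safety table, show how many dose-3 recipients had this contact. Count those without it as missing, not as having no event.

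The cost is one short extra data entry per dose-3 recipient (at most 80) and a protocol amendment, which section 10 requires for anything beyond administrative changes. The recorded reaction rate after dose 3 may rise. A participant diary card at every dose would be a reasonable option, but it goes beyond the gap shown, since doses 1, 2 and 4 already have collection at one month.
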